4.11.3. Change from Baseline in %-predicted FEV₁

The descriptive statistics of %-predicted FEV₁, absolute, and relative change in %-predicted FEV₁ will be summarized for each visit for the ITT population. The highest FEV₁ assessment at each visit will be included into the analyses.

4.11.4. Pulmonary Exacerbation Rates

The descriptive statistics of the 48-week pulmonary exacerbation rates based on different definitions in Section 5.6 will be reported for the ITT population. The number of subjects with 0, ≥ 1 , ≥ 2 , and ≥ 3 pulmonary exacerbations based on different definitions will also be tabulated as well.

4.12. Tertiary Analyses

4.12.1. FVC

The absolute change in FVC will be analyzed using descriptive statistics for each visit for the ITT population.

4.12.2. Body Weight, Height, and BMI

Descriptive statistics on change from baseline in the body weight (kg), height (cm), and BMI will be displayed at each visit for the As-Treated population.

The change in weight or height percentiles calculated by using Centers for Disease Control and Prevention (CDC) growth chart [CDC] will be analyzed similarly for subjects < 18 years old at baseline.

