#### **14.1.2. Inclusion of Minors**

Inclusion of both children and adults in this protocol is appropriate and necessary. Based on past experience in multiple randomized clinical trials [[Fuchs 1994](#), [Ramsey 1999](#), [Saiman 2003](#), [Elkins 2006](#)], including the double-blind study of ataluren in nmCF [[Rowe 2012](#)], there is strong precedence for this approach. The benefit-risk ratio is enhanced by inclusion of only children with FEV1 values ≤ 90% of predicted, weighting enrollment toward those who are already experiencing CF-related pulmonary compromise. In addition, this ratio is enhanced by the known severity of the disease phenotype in patients with CF caused by nonsense mutations [[Shoshani 1992](#), [Cystic Fibrosis Genotype-Phenotype Consortium 1993](#), [Kerem 1996](#), [de Gracia 2005](#), [McKone 2006](#)], the generally favorable safety profile of ataluren, and the limited

population of patients with nonsense-mutation-mediated disease (10% of the total CF population).

Inclusion of children as well as adults will allow an understanding of how age-dependent disease characteristics may affect treatment outcomes. A total of 65 (86.7%) patients <18 years of age completed Study 009 and are eligible for this open-label extension study. Participation of these younger patients in this extension study will allow further exploration of the influence of age on safety and efficacy outcomes. Study participants will now be at least 9 years of age, enhancing the ability of participants to reliably perform protocol procedures [Loeb 2008] and will have nomogram data describing %-predicted FEV1 values [Wang 1993].

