2.2.3. Tertiary Objectives

The tertiary objectives are to determine the efficacy of ataluren as assessed by other parameters of pulmonary function (FVC and FEF₂₅₋₇₅), and changes in body weight BMI.

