2.3.3. Tertiary Endpoints

- Change from baseline to end of treatment in spirometric performance as measured by FVC and FEF₂₅₋₇₅
- Change from baseline to end of treatment in body weight and BMI

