3. STUDY POPULATIONS

3.1. As-Treated Population

The As-Treated population consists of all subjects who received at least 1 dose of ataluren. This population will be evaluated in the analyses of safety and treatment administration.

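### BMI is a named tertiary efficacy endpoint, but SAP 4.12.2 pools its raw change over minors and adults and, unlike weight and height, gives it no age-standardised summary for subjects under 18.

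*SAP*

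**What the plan says.** The tertiary objective in SAP 2.2.3 is to assess efficacy by further lung-function measures "and changes in body weight BMI". The matching endpoint in SAP 2.3.3 is "Change from baseline to end of treatment in body weight and BMI". Height is not an endpoint.

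The analysis is in SAP 4.12.2: descriptive statistics on "change from baseline in the body weight (kg), height (cm), and BMI will be displayed at each visit", for the As-Treated population. SAP 3.1 defines that population without regard to age: "The As-Treated population consists of all subjects who received at least 1 dose of ataluren". A second sentence in 4.12.2 adds an age-standardised display: "The change in weight or height percentiles calculated by using Centers for Disease Control and Prevention (CDC) growth chart" "will be analyzed similarly for subjects < 18 years old at baseline". It names weight and height, not BMI.

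On who is enrolled, Protocol 14.1.2 wants both children and adults and says "Study participants will now be at least 9 years of age". Protocol 14.2.9.3 justifies measuring weight and BMI on the ground that people with CF tend to weigh less than healthy people matched on sex and age.

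**The concern.** A minor who follows the same growth curve throughout gains BMI in raw units with no change in nutritional status. An adult in the same position shows no change. One mean over both groups therefore contains a growth component that depends on the share of minors and on time in the study. There is no control arm in which the same growth would appear and cancel.

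For weight, the CDC percentile display lets a reader see whether minors gained relative to their peers. For BMI no display does this. A raw BMI rise in minors is compatible with a rising, stable or falling position relative to peers of the same age, and the planned tables could not tell these apart. Yet position relative to peers is the comparison on which the protocol rests its case for measuring BMI.

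**Working it through.** **Is BMI standardised anywhere else?** The places where it might be are these.

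- SAP 4.12.2: percentiles for weight and height only.
- SAP 4.11.1: an optional breakdown of vital signs by age group, to be done as necessary. The vital-sign parameters listed there are blood pressure, heart rate, oximetry and temperature. Weight-change categories appear in that section, but BMI does not.
- SAP 4.6: defines age groups <18 and ≥18 years, for baseline tables only.
- Protocol 11.4.7.2: weight and BMI summarised by visit with change from baseline; no standardisation.
- SAP 6: lists the changes from the protocol; BMI is not mentioned, so no reason for the gap is given.

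The SAP allows for age elsewhere: blood pressure in minors is judged against age and height nomograms (4.11.1), heart-rate limits are banded by age (4.11.2), and FEV1 is analysed as %-predicted (4.11.3). BMI is the exception.

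**How large could the growth component be?** The plan gives no figure to reproduce, so this is illustration only.

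Pooled mean change from growth alone = f × g × t, where

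- f = share of minors (assumed 0.2 to 0.6; the enrolled number is not stated);
- g = yearly BMI growth in minors with no drug effect (assumed 0.2 to 0.8 kg/m2);
- t = weeks × 7 / 365.25;
- adult change is assumed to be 0.

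| Visit | t (years) | Low: 0.2 × 0.2 × t | High: 0.6 × 0.8 × t |
|---|---|---|---|
| Week 48 | 0.92 | +0.04 kg/m2 | +0.44 kg/m2 |
| Week 96 | 1.84 | +0.07 kg/m2 | +0.88 kg/m2 |
| Week 192 | 3.68 | +0.15 kg/m2 | +1.77 kg/m2 |

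The only related count is in Protocol 14.1.2: 65 patients under 18 (86.7%) completed Study 009 and are called eligible. Since 65/0.867 ≈ 75, this suggests about 75 minors among the 238 patients in Study 009, or 75/238 ≈ 32%. That is not the share in this study. Some will since have turned 18, particularly as most eligible patients were expected to have passed through the 96-week Study 009e, and the documents do not say who enrolled.

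SAP 2.1 records premature termination on 2 March 2017, with ongoing subjects discontinued. The later rows may therefore hold few subjects or none.

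**What would an age-standardised measure show?** A minor who stays on the same BMI-for-age percentile contributes 0 at every visit, whatever f, g and t are.

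**The case against.** A reader might infer that the plan will report normal growth as improvement. The documents do not support that. SAP 4.2 calls all analyses descriptive. Protocol 11.4.7.2 sets no test and no rule that a gain is a benefit, and Protocol 14.2.9.3 itself calls changes in weight and BMI nonspecific. SAP 4.11.1 tabulates weight gain of 10-<20% and ≥20% as Grade 2 and Grade 3, which treats it as a safety finding.

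A reader might also infer that weight is as badly served as BMI. It is not: the percentile analysis for minors is in the same section, and the raw kilogram table is a companion to it.

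Three further objections carry weight. The size of the growth component rests wholly on assumed inputs, and termination cuts the time over which it builds up. Age-standardised BMI would remove normal growth but would not supply a control arm, so it would not make the BMI result evidence of efficacy. And nothing is lost for good: height and weight are measured at each clinic visit and by-subject listings are planned (SAP 4.1), so BMI-for-age can be derived later.

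These points limit the severity and the claim about weight. They do not answer the gap for BMI: a descriptive table should still be interpretable for the objective it serves.

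**Conclusion.** The point holds in a narrow form. BMI is a named tertiary endpoint, its raw change is pooled over minors and adults, and neither document plans an age-standardised version. In this single-arm study the pooled BMI change cannot separate growth from a drug effect. For weight, only the pooled raw table is affected.

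The direction of the growth component is upward, assuming that enrolled minors gain BMI as they grow. Its size is unknown, and the tabulated ranges show only how it scales with the assumptions. Severity is minor: the endpoint is tertiary, the analysis descriptive, and the missing summary recoverable from collected data.

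**What to change.** In SAP 4.12.2:

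1. Add change from baseline in CDC BMI-for-age percentile (or z-score) by visit for subjects under 18 at baseline, alongside the planned weight and height percentiles.
2. Show raw BMI and raw weight change separately for <18 and ≥18 years at baseline, using the groups in SAP 4.6. For weight, this split is all that is needed.

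The cost is one more variable, derived from height, weight, age and sex, all already collected, and smaller cells in a study of about 70 subjects. SAP 1 allows refinements by amendment before database lock.

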#### **14.2.9.3. Weight/Body Mass Index**

Patients with CF are generally underweight compared to healthy individuals of the same gender and age [Rabin 2004]. Assessment of body weight and BMI during the course of this Phase 3 study is planned. While changes in these parameters are quite nonspecific, they constitute simple-to-assess outcomes of general well-being.

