4. STATISTICAL AND ANALYTICAL PROCEDURES

4.1. General Statistical Considerations

By-subject listings will be created for each CRF module. Summary tables for continuous variables will contain the following statistics: n, mean, standard deviation, standard error, and 95% confidence intervals (CIs) on the mean, median, minimum, and maximum. Summary tables for categorical variables will include N, n, percentage, and 95% CIs on the percentage. Where applicable, the summary data (mean, standard error) will be presented in graphical form by time of visit.

The baseline value used in each analysis will be the last (most recent) non-missing pretreatment value, except as noted for spirometry data.

Unless otherwise specified, all applicable analyses will be 2-sided at the 0.05 level of significance.

All analyses and tabulations of data will be performed using SAS (Version 9.1 or higher).

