4.11. Secondary Analyses

4.11.1. Vital Signs

Vital sign parameters include systolic blood pressure (mmHg), diastolic blood pressure (mmHg), heart rate (bpm), pulse oximetry (%), and body temperature (°C). Vital sign assessments and the changes from baseline for each parameter will be summarized by visit for the As-Treated population. Maximal and minimal change from baseline in each parameter will also be summarized.

Weight gain and loss will be tabulated for the following categories: normal change from baseline, weight gain (5-<10%), weight gain (10-<20%) (Grade 2), weight gain (\geq 20%) (Grade 3), weight loss (5-<10%) (Grade 1), weight Loss (10-<20%) (Grade 2), and weight loss (\geq 20%) (Grade 3).

For adults (\geq 18 years of age), blood pressure parameters will be programmatically flagged for Stage 1 hypertension (systolic: \geq 140 to <160 mmHg, diastolic: \geq 90 to <100 mmHg), Stage 2 hypertension (systolic: \geq 160 mmHg, diastolic: \geq 100 mmHg), and hypotension (systolic: <90 mmHg, diastolic: <60 mmHg) [USDHHS 2003]. For children and adolescents (<18 years of age), blood pressure parameters will be programmatically evaluated based upon height- and age-specific nomograms, and categorized by percentile (<95%, \geq 95% to <99%, and \geq 99%) [USDHHS 2005]. A summary of the number and percent of subjects by systolic and diastolic blood pressure categories of <95%, \geq 95% to <99%, and \geq 99% as defined as follows.

<95%: for age <18 years old, SBP <95% and DBP <95%; for age \geq 18 years old, SBP <140 mmHg and DBP <90 mmHg.

\geq 95% to <99%: for age <18 years old, SBP \geq 95% to <99% or DBP \geq 95% to <99%; for age \geq 18 years old, SBP \geq 140 to <160 mmHg or DBP \geq 90 to <100 mmHg. In addition, none of SBP and DBP meets the following criteria of \geq 99%.

\geq 99%: for age <18 years old, SBP \geq 99% or DBP \geq 99%; for age \geq 18 years old, SBP \geq 160 mmHg or DBP \geq 100 mmHg.

Shift tables will be presented showing change in results from baseline using above <95%, \geq 95% to <99%, and \geq 99% categories.

As necessary, vital signs will be described by duration of study drug exposure, by dose, by age group, by sex, by race, by weight, and for special populations (eg, antibiotic use).

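### Growth in minors is summarised as change in CDC percentile, a scale on which equal z-score changes count unequally and very underweight children add little to the mean

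*SAP*

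**What the plan says.** SAP 4.12.2 plans two kinds of growth summary. For everyone in the As-Treated population: "Descriptive statistics on change from baseline in the body weight (kg), height (cm), and BMI will be displayed at each visit". For minors it adds: "The change in weight or height percentiles calculated by using Centers for Disease Control and Prevention (CDC) growth chart [CDC] will be analyzed similarly", restricted by "for subjects < 18 years old at baseline". The descriptive statistics are those of SAP 4.1: "n, mean, standard deviation, standard error, and 95% confidence intervals (CIs) on the mean, median, minimum, and maximum". SAP 4.1 also provides by-subject listings for each CRF module.

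SAP 4.11.1 tabulates weight gain and loss as a percentage of baseline weight, for example "weight loss (5-<10%) (Grade 1), weight Loss (10-<20%) (Grade 2").

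Neither document mentions a z-score, and no BMI percentile is planned. Protocol 14.2.9.3 explains the interest in weight: "Patients with CF are generally underweight compared to healthy individuals of the same gender and age". On numbers, Protocol 14.1.2 says: "A total of 65 (86.7%) patients <18 years of age completed Study 009 and are eligible for this open-label extension study"; how many of them enrolled here is not stated. Weight and BMI are tertiary endpoints (SAP 2.3.3), and SAP 4.2 describes all analyses as descriptive.

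**The concern.** A child's percentile is a cumulative probability. Near the median a modest change in relative size moves many percentile points; far from the median the same change moves very few. A mean of percentile changes therefore weights children by where they start on the chart. For a population described as generally underweight, the children who lose weight in that average are those whose growth a measure of general well-being should be able to show.

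This matters because of what the other summaries cannot show. Treatment was planned for 192 weeks, and children gain kilograms and centimetres over such a period simply by growing. A positive change in kg or cm does not show that a child has kept pace with peers. Only an age- and sex-referenced measure can, and percentile change is the only one planned. There is no control arm against which a distortion of scale would show up.

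**Working it through.** The plan states no effect size, variance or power for this analysis, so there is no figure of its own to reproduce. The check concerns the scale.

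**Relation used.** The z-score is the inverse normal of the percentile, so percentile P(z) = 100·Φ(z). The starting z values, spreads and group sizes below are assumptions, because neither document gives a baseline distribution.

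**1. Compression.** Change for a loss of 0.5 z = P(z - 0.5) - P(z). The local weight of a child relative to one at the median is the ratio of slopes, exp(-z²/2).

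| Baseline z | Percentile | Change for a 0.5 z loss (points) | Local weight |
|---|---|---|---|
| 0 | 50.0 | -19.1 | 1.00 |
| -0.5 | 30.9 | -15.0 | 0.88 |
| -1 | 15.9 | -9.2 | 0.61 |
| -1.5 | 6.7 | -4.4 | 0.32 |
| -2 | 2.3 | -1.7 | 0.14 |
| -2.5 | 0.6 | -0.5 | 0.04 |

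**2. Share of the summary.** In simulation with baseline z ~ N(-1, 1) and zero-mean individual change of SD 0.3 to 0.5, children below the 5th percentile are 26% of the group but supply about 6 to 7% of the total absolute percentile change. With N(-1.5, 1) they are 44% and supply 11 to 13%.

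**3. Sign of the mean.** Suppose half the children start at z = -2 and lose 0.5, and half start at z = 0 and gain 0.2.
- z scale: (-0.5 + 0.2)/2 = -0.15.
- Percentile scale: P(-2.5) - P(-2) = -1.65 and P(0.2) - P(0) = +7.93, so the mean is (-1.65 + 7.93)/2 = +3.1 points.

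The mean relative position has fallen, yet the reported mean rises.

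**4. Is there also an upward drift?** Take baseline z ~ N(μ, σ²) and independent zero-mean change with SD s. The expected percentile change is 100·[Φ(μ/√(1+σ²+s²)) - Φ(μ/√(1+σ²))].
- μ = -0.5, σ = 1, s = 0.3: Φ(-0.346) - Φ(-0.354) gives +0.3 points.
- μ = -1.5, σ = 0.8, s = 0.5: Φ(-1.091) - Φ(-1.171) gives +1.7 points.

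The range over μ from -0.5 to -1.5, σ from 0.8 to 1 and s from 0.3 to 0.5 is therefore about +0.3 to +1.7 points. For an assumed 20 minors (μ of -1 or -1.5, σ = 1), the standard error of the mean is about 1.4 to 2.8 points. The formula makes the spread of z grow from σ² to σ² + s². If instead both visits carry equal independent noise around an unchanged z, the expected drift is zero (simulated -0.01 to +0.02).

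**5. What the other summaries show.** A child who gains no weight for a year loses 0% of baseline weight and falls in the normal-change category of SAP 4.11.1. One who gains less than peers shows a positive change in kg. Neither summary registers the fall in relative position.

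**The case against.** The strongest reply is that this is a question of scale in a supplementary display. Protocol 11.4.7.2 asks only for weight and BMI and their changes; the percentile summary is an addition by the SAP. The endpoint is tertiary, no test or decision uses the mean, and Protocol 14.2.9.3 itself treats these measures as nonspecific. That stands, and it limits the importance of the point.

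It can also be said that the mean is not shown alone. The median, minimum, maximum and by-subject listings are planned, and a very underweight child who actually loses weight is counted fully in the percent-loss categories. This stands in part. Each child's percentile change has the same sign as the z change, so the median is much less exposed to the reversal in step 3. But a median does not show a faltering minority, and the minimum shares the fault: a child at the 2.3rd percentile cannot fall by more than 2.3 points, so the minimum will tend to come from children nearer the median. The gap that remains is the child who falls behind peers without losing weight.

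Four stronger readings are tempting and are not supported.
- A reader might infer that random variation will appear as improvement. It does so only if z-scores spread out after baseline; equal noise at both visits gives no drift.
- A reader might infer that the protocol places these patients in the low tail. It says only that CF patients are generally underweight, and nothing about height.
- A reader might infer that the best-nourished children dominate the mean. The slope is steepest at the median and the upper tail is compressed equally, so children nearest the median dominate.
- A reader might infer that faltering becomes invisible. The listings and loss categories rule that out as a general statement.

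**Conclusion.** The point holds as one about scale. Mean change in CDC percentile gives a child at z = -2 about 0.14 of the weight of a child at the median, and under plausible mixtures it can differ in sign from the mean z change. No other planned summary is age-referenced, so nothing else in the tables fills the gap.

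The algebra in steps 1 and 3 is exact for the stated starting values. How much it matters in this cohort is not known, because no baseline percentiles are given: if most minors lie at z = -0.5 to -1, their local weight is still 0.88 to 0.61 and the distortion is moderate; it is severe only for those near z = -2 or below. The possible upward drift is secondary, conditional on z-scores diverging after baseline, and about 0.3 to 1.7 points under the assumed values. No conclusion on the primary safety objective depends on any of this. It is an inexpensive improvement to a tertiary, descriptive analysis.

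**What to change.** In SAP 4.12.2, add mean change from baseline in weight-for-age and height-for-age z-score, from the same CDC reference, as the age-standardised summary for subjects under 18 at baseline. Compute the z-scores before any rounding of percentiles: the SAP does not say how percentiles are stored, and an inverse normal taken from a rounded low percentile is unstable, and undefined at zero, in exactly the children of interest. Keep the percentiles as a descriptive display.

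The cost is one sentence of SAP text and one further derived variable per measure, with no new data. SAP Section 1 allows refinements by amendment before database lock.

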4.13. Pharmacokinetics Analyses

The ataluren plasma concentrations collected prior to the morning dose will be listed.

For ataluren plasma concentrations, those that are below the limit of quantification will be identified by “BQ” in listings. Those values that are missing will be left blank in listings.

4.14. Interim Analyses

Interim safety analyses are planned when ~35 subjects have completed ≥ 32 weeks of treatment and when ~35 subjects have completed ≥ 64 weeks of treatment. Additional interim safety analyses may be performed based on the discretion of the DMC and will be described in the DMC charter. Based on the results of its deliberations, the DMC can recommend continuation of the study unchanged, study interruption, study termination, modification of the study, or alteration in the DMC monitoring plan.

The planned interim analysis will be based on the DMC Charter focusing on the safety review.

5. DATA HANDLING

5.1. Baseline

In general, Baseline is defined as the last non-missing valid assessment prior to or on the date of the first dose. However, Baseline for FEV₁, %-predicted FEV₁, FVC, or FEF₂₅₋₇₅ is the average of the corresponding valid assessments at Screening and Week 1 visit if they met ATS criteria.

5.2. Analysis Visits

Analysis visits are the scheduled visits in the protocol, unless specified otherwise. They are not derived via visit window mapping. Baseline is derived as noted in Section 5.1. Final Visit is derived as the last non-missing on-treatment visit during the study for each subject and included into the by-visit summary analyses. Early termination visit should also be derived as the visit right after the non-missing scheduled visit. For example, if the subject discontinued after Week 8, the early termination visit should be derived as Week 16.

